Does the use of a customized titanium reconstruction plate for orbital fractures result in better orbital volume and outcomes?

NCT03673865

Date: February 04, 2020
IRB00103655

Protocol

TITLE

Does the use of a customized titanium reconstruction plate for orbital fractures result in better orbital volume and outcomes?

ABSTRACT

Facial fractures are among the most common traumas in level one trauma centers. ^(1, 2) Approximately 10–25% of facial fractures involve the orbit. ⁽³⁾ Orbital fracture reconstruction is challenging due to the complex bony anatomy and the proximity of adjacent vital structures. In orbital fracture reconstruction, the immediate clinical outcome is challenging to assess due to postoperative edema. Orbital volume measurements remain the only objective method to evaluate reconstruction in the immediate post-operative period.

Studies have shown a linear correlation between post-traumatic orbital volume and enophthalmos. ⁽⁴⁾ The timely and accurate restoration of orbital volume has been demonstrated to substantially reduce complications including enophthalmos, diplopia, and blindness due to orbital compartment syndrome compared with methods that do not assess orbital volume. ⁽⁵⁻⁷⁾ The use of intra-operative CT scanning and navigation to correctly establish intra-operative orbital volume have been described but are time-consuming and expensive. ⁽⁸⁾ A patient-specific orbital implant utilizing virtual surgical planning (VSP) has also been advocated. ⁽⁹⁾ The use of office-based 3-dimensional printers (OB3DP) is evolving, and these inexpensive devices can be used to create a realistic 3D model of the patient's orbital fracture as well as the contralateral healthy orbit. This allows the surgeon to adapt a stock reconstruction orbital plate to the specific injured orbit and to recreate the normal preoperative orbital volume.

The purpose of this study is to answer the following clinical question: among patients with orbital fractures, does the use of pre-adjusted (pre-bend) patient-specific implants utilizing OB3DP technology more accurately reconstruct normal orbital volumes when compared with the use of standard non-adapted orbital implants?

SPECIFIC AIMS AND HYPOTHESIS

Aim #1: To compare orbital volume restoration at immediate post-operative hour

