The primary outcome variable is the orbital volume of the injured orbit compared to the contralateral uninjured orbit as assessed by CT scan with OsiriX medical imaging software (OsiriX MD 8.5.2) **at immediate post-operative hour**.

Accordingly, the primary outcome variable will be classified as:

- A. The absolute reduction in orbital volume from the measured post-traumatic volume, as measured by CT.

The secondary outcome variables will be recorded 1 week, 3 weeks, and 6 weeks postoperatively.

The secondary outcome variables include the following:

- 1- Adequate orbital volume reduction, defined as a reduction of orbital volume to **less than 2 cm³**.
- 2- Unsatisfactory orbital volume, defined as a final orbital volume **more than 2 cm³**
- 3- Post-operative variables: enophthalmos, infection, infraorbital nerve injury, traumatic pupillary mydriasis, orbital compartment syndrome, extra-ocular motility, and plate contour.
- 4- Operating time.
- 5- Length of stay (LOS).
- 6- Treatment charges.

The following are details regarding secondary outcome variables:

- Enophthalmos as assessed by clinical examination using a Hertel exophthalmometer.
 - A difference of more than 2 mm between the two orbits is diagnostic for enophthalmos.⁽⁴⁾
- Infection
 - As defined by the presence of post-operative pus in the wound, a sinus tract or fistula, or elevated WBC >11.0x10⁹/L combined with erythematous skin and swelling on the operated side more than on the un-operated side.
- Infraorbital nerve injury as assessed by clinical examination using neurosensory testing (NST).
 - i. NST is a standardized methodology designed to objectively evaluate sensory nerve function.⁽²²⁾ The sensory impairment is determined by 3 levels of testing; each level classifies a specific type of sensory nerve injury.^(22, 23)
 - ii. All patients will be assessed for the development of altered sensation of the infra-orbital nerve that:
 - A. Did not present prior to the surgery.
 - B. Did not improve after the surgery.
- Traumatic pupillary mydriases as assessed by pupillary size measurement in millimeters.
 - All patients will be assessed for the development of post-operative traumatic pupillary mydriasis that did not present prior to the surgery.
- Orbital compartment syndrome as assessed through clinical examination using tonometers.
 - Intra-ocular pressure (IOP) > 40 mmHg is diagnostic of orbital compartment syndrome.

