- Extra-ocular motility as assessed through clinical examination. The patient should be able to move the eyes through the six cardinal positions of gaze (left, right, up and right, up and left, down and right, down and left). All patients will be examined for the following:
 1. Development of restricted extraocular motility that was not present prior to the surgery.

2. Persistent restriction of extraocular motility after the surgery.

- Plate contour
 - Inability to achieve the normal orbital contour as assessed in the immediate post-operative CT scan.
- Operating time
 - This will be calculated from fracture exposure and identification to the final implant placement and fixation and will be recorded in minutes.
- Length of stay
 - 1- Isolated orbital floor fracture patients do not require a pre-operative hospital stay. Length of stay will be calculated in terms of post-operative hospital stay (days).
 - 2- Length of stay in cases of complex orbital fracture will be calculated in terms of pre-operative and post-operative hospital stay (days).
- Treatment charges

This will be calculated with consideration of the following:

- 1- Facility operating room charges, which include anesthesia time (surgical time multiplied by the facility rate of \$33/ minute).
- 2- Hardware charges (plates and screws).
- 3- LOS charges (LOS multiplied by the facility daily rate of \$1,690/ day).
- 4- The cost of the 3D printed model including the cost of the 3D printer and filaments (\$1.5).

All treatment charges variables will be provided by the GMH Financial Planning and Analysis center. Total treatment charges facility operating room charges, hardware charges, LOS, and the 3D printed model cost will be compared between groups in a manner similar to that outlined by Bouloux et al. ⁽²⁴⁾

Randomization Sample Size & Calculation

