We expect a **sample size of 60** surgical cases, evenly split between the new treatment and control groups, to have a study powered to **detect at least a 1 cm³ difference in orbital volume** between the groups. The sample size calculation was based on using a two-sample Student's t-test to compare the difference in contralateral orbital volume between the treatment and control groups. We used a **power of 90%**, alpha level of .05, and 1.17 cm³ standard deviation of orbital volume. The 'normal' orbital volume and standard deviation were estimated from the results of Forbes et al. (1984). Sample size calculations were performed with the 'power.t.test' function in R statistical software based on Cohen (1988).⁽²⁵⁾ Taking attrition into account, if 25% of our expected patient enrollment numbers are not met for any reason, **our study would still retain a power of 80%**. Additionally, in the event of attrition from loss-to-follow-up alone, our primary outcomes variable and the bulk of the secondary outcomes variables, including the reduction of orbital volume to less than 2 cm³, operative time, traumatic pupillary mydriasis, orbital compartment syndrome, extra-ocular motility, and plate contour, will be successfully obtained on immediate post-operative hour. **Attrition at these stages will have no effect on the above variables.**

Randomization & Statistical Analysis

Cases will be randomized to the treatment or control arms using a pre-generated block randomization scheme with a **block size of 4** and stratified according to surgeon/specialty. In essence, each surgeon will receive their own list of randomized cases to simplify the logistics of the trial. **The block randomization guarantees that at no point during the trial will there be more than a 3-case difference between the treatment and control arms for each individual surgeon**; thus, it is possible but unlikely that there will be a maximum 9 case difference at some

point (sizes will be equal at completion). The randomization scheme has been pre-generated by a statistician, and the resulting trial arm for each case will be placed in envelopes to be revealed at the time of patient enrollment. The treatment will not be blinded to the physician or the patient; it is not practical to keep knowledge of the procedure concealed.

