- Complex orbital fractures will be exposed and identified via a transconjunctival approach in combination with lateral cantholysis if needed to improve access.
- To record and compare the operative time between the two groups, a stopwatch will be utilized. The time in minutes will be recorded from fracture exposure and identification to final implant placement and fixation.

Postoperative Assessment

During post-operative care, all patients will undergo the following:

- 1) Maxillofacial non-contrast CT scans according to the protocol will be obtained as part of the standard of care in managing orbital fractures.
- 2) The PI will evaluate the orbital volume using OsiriX (medical software). Orbital volume measurements will be obtained to compare the injured and uninjured (contralateral) orbital volumes. OsiriX MD offers advanced processing techniques and has the ability to precisely measure orbital volume. It utilizes the DICOM data from the immediate post-operative CT scans.
- 3) All patients, regardless of the group into which they are randomized, will receive their post-operative assessment by the designated team resident under the supervision of one of the following attendings: [name] for OMFS, [name] for ENT, or [name] for Plastic Surgery.
- 4) All patients, regardless of the group into which they are randomized, will receive their post-operative ocular assessment by [name], ophthalmology attending and Co-PI, or by her fellow [name].

Follow-Up

- All patients will be regularly assessed at 1 week, 3 weeks, and 6 weeks postoperatively.

This is a standard post-operative follow-up schedule for craniomaxillofacial fracture patients. It is also an adequate duration for edema to resolve, which will assist in the accurate evaluation of enophthalmos. The following will be evaluated and recorded by the surgical team at each follow-up visit: enophthalmos, infection, infraorbital nerve injury, traumatic pupillary mydriasis, orbital compartment syndrome, and restricted extra-ocular movement.

- In terms of data collection and data extraction from Epic: PI [name], co-PI [name] and an assigned research coordinator will be involved.

Patient Compensation

All patients enrolled in the study will be compensated with \$100 for their time and to encourage compliance. Their compensation includes the costs of participation in the study (\$50) and the completion of the follow-up visits at week 6.

Data Collection & Analysis

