Data	Time
Age, sex, race, DOB	Pre-operative (pre-op)
Mechanism of injury, time from injury to admission	Pre-op
Type of orbital fracture and other injuries	Pre-op
Indications for surgery	Pre-op
CT scans results (fracture size & location)	Pre-op
Extra-ocular motility indicating which gaze	Pre-op
Level of infraorbital nerve injury	Pre-op
Traumatic pupillary mydriasis	Pre-op
IOP (Intra-ocular pressure)	Pre-op
Enophthalmos (Hertel exophthalmometer measurement)	Pre-op
The use of 3D printed models	Pre-op
The time needed to print the model	Pre-op
Orbital and ocular exam results	Pre-op
Time from admission to surgery	Pre-op
Date of surgery	Pre-op
Length of surgery (minutes)	Operative
Approach	Operative
Intra-operative complications	Operative
Post-operative orbital volume comparison (OsiriX)	Post-operative
Dates of post-operative visits	Post-operative, weeks 1, 3, and 6
Extra-ocular motility indicating which gaze	Post-operative, weeks 1, 3, and 6
Level of infraorbital nerve injury	Post-operative, weeks 1, 3, and 6
Traumatic pupillary mydriasis	Post-operative, weeks 1, 3, and 6
IOP (Intra-ocular pressure)	Post-operative, weeks 1, 3, and 6
Infection	Post-operative, weeks 1, 3, and 6
Enophthalmos (Hertel exophthalmometer measurement)	Weeks 1, 3, and, 6

Overall cost	Post-operative
Need for second surgical procedure	Post-operative, weeks 1, 3, and 6

SIGNIFICANCE AND INNOVATION

This project will test two new and evolving methodologies in the medical world: 1) an office-based 3D printer and 2) pre-adjusted patient-specific implants. These two methodologies have yet to be applied together in orbital fracture reconstruction. Additionally, this study focuses on low-income patients and will be the first of its kind serving this population. Several other benefits include potential savings related to total overall cost, a reduced operative time and postoperative course, and a subsequent increase in both the quality of care and the value of care, especially in the underserved patient population cared for at GMH. We expect the results of this study to be applicable at most major urban trauma centers across the USA and abroad. The results of this study can be used in future studies as a model or pilot study.

FUTURE PLANS

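### The plan says loss to follow-up cannot affect mydriasis, orbital compartment syndrome and motility, yet it also records all three at weeks 1, 3 and 6, and inclusion item 9 undercuts the statement for every outcome

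*Combined protocol and SAP*

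**What the plan says.** The section Randomization Sample Size & Calculation argues that loss to follow-up leaves the primary outcome and six named secondary outcomes untouched. The secondary outcomes are volume reduction below 2 cm³, operative time and these: "traumatic pupillary mydriasis, orbital compartment syndrome, extra-ocular motility, and plate contour, will be successfully obtained on immediate post-operative hour". It concludes: "Attrition at these stages will have no effect on the above variables".

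Other sections give a different or additional timing:

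- **Methodology, outcome definitions:** "The secondary outcome variables will be recorded 1 week, 3 weeks, and 6 weeks postoperatively". Item 3 of the list that follows contains "enophthalmos, infection, infraorbital nerve injury, traumatic pupillary mydriasis, orbital compartment syndrome, extra-ocular motility, and plate contour".
- **Methodology, detail on motility:** one of the two findings to be recorded is "Persistent restriction of extraocular motility after the surgery".
- **Follow-Up:** the surgical team records at each visit "enophthalmos, infection, infraorbital nerve injury, traumatic pupillary mydriasis, orbital compartment syndrome, and restricted extra-ocular movement".
- **Data Collection & Analysis table:** motility, mydriasis and intra-ocular pressure are each scheduled at "Post-operative, weeks 1, 3, and 6".
- **Abstract:** after orbital reconstruction, "the immediate clinical outcome is challenging to assess due to postoperative edema".

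Inclusion & Exclusion Criteria, inclusion item 9, admits only subjects who came back for the six-week visit. Randomization & Statistical Analysis names tests for binary complications. It gives no analysis time for them and no rule for missed visits.

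**The concern.** An outcome is protected from loss to follow-up only if its analysed value is complete before patients can be lost. Three clinical outcomes are declared protected, yet they are examined again at three later visits, and the plan does not say which reading is analysed. If the later readings count, missing values at those visits matter, and the plan has declared them harmless in advance. If only the early reading counts, the plan should say so.

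These outcomes feed Hypothesis 2, that the pre-adjusted implant gives fewer complications. With no analysis time fixed, the analyst could choose among up to four readings (post-operative and weeks 1, 3 and 6) after seeing the data. Patients who do not return may differ from those who do, and possibly differently in the two arms, since neither patient nor surgeon is blinded.

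Item 9 raises a wider issue. A criterion that can be met only six weeks after surgery cannot be checked at enrolment. It acts as a filter on who is analysed, and that filter would also reach outcomes measured in theatre or on the immediate CT.

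**Working it through.** **1. The plan's own figures.** Inputs from the sample-size section: difference 1 cm³, SD 1.17 cm³, alpha 0.05 (taken as two-sided, since sidedness is not stated), 60 patients split evenly. For a two-sample t-test the noncentrality is (1/1.17) × √(n/2), with n per arm.

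- n = 30: 0.855 × √15 = 3.31, with 58 degrees of freedom; power 90.2%. The plan states 90%.
- 25% shortfall: 60 × 0.75 = 45, so n = 22.5: 0.855 × √11.25 = 2.87, with 43 degrees of freedom; power 80.0%. The plan states 80%.

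Both figures reproduce. They concern only the t-test on orbital volume and offer no protection to binary clinical outcomes.

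**2. Timing of the outcomes in the attrition statement.**

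| Outcome | Timing elsewhere in the plan | Protected on timing? |
|---|---|---|
| Orbital volume, including the 2 cm³ criterion | Immediate CT | Yes |
| Plate contour | Immediate CT | Yes |
| Operative time | Stopwatch in theatre | Yes |
| Mydriasis | Post-operative and weeks 1, 3, 6 | Only for the early reading |
| Compartment syndrome (intra-ocular pressure) | Post-operative and weeks 1, 3, 6 | Only for the early reading |
| Motility | Post-operative and weeks 1, 3, 6 | Only for the early reading |

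So three of the six named secondary outcomes have the stated property only if three scheduled readings are set aside. No section sets them aside.

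**3. Effect of item 9.** If item 9 defines who is analysed, a patient lost before week 6 contributes nothing, even with a valid immediate CT. If, for illustration, 25% were lost this way, the primary analysis would fall from 60 to 45 patients and its power from 90.2% to 80.0%. The three rows marked Yes would then lose their protection as well.

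**4. Illustrative bounds for a missing binary outcome.** Let m be the fraction missing in an arm, r the rate among those seen and u the unknown rate among those missing. The arm's rate is (1 − m)r + mu, with u anywhere from 0 to 1, so it can lie anywhere in an interval of width m. With m = 0.25 in both arms, each rate is bounded to a width of 0.25 and the difference to 0.25 + 0.25 = 0.50. The 25% is borrowed from the plan's enrolment shortfall. It is not a forecast of loss to follow-up, and the same widths apply to any binary outcome with that much missing.

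**The case against.** The strongest reply is that repeated readings do not exclude one another. The data table lists a post-operative reading besides weeks 1, 3 and 6, so an early value may well exist, and it would survive later loss. The table gives enophthalmos only at weeks 1, 3 and 6, and the attrition statement leaves enophthalmos out, which suggests that the authors separated it deliberately. The outcome section's sentence on timing is also loose, since its list includes operating time and plate contour. All of this stands. It shows that the statement could be true of an early reading; it does not show that the early reading is the endpoint.

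A reader might also infer that a reading in the first hour is worthless because of edema, or that persistent restriction cannot be judged then. The documents do not establish either. The Abstract's remark on edema is general, and the Follow-Up section links edema resolution to enophthalmos only. Persistent restriction can mean restriction present before surgery and still present after it, with no stated duration. The edema remark is therefore supporting evidence only.

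It is also fair that the sentence sits in the sample-size justification, that no analysis rule invokes it, that the outcomes are secondary and unpowered, and that part of the patient payment is tied to the week-6 visit. These points limit the consequence without making the statement correct.

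**Conclusion.** The point holds and should be corrected. For mydriasis, orbital compartment syndrome and motility, the no-effect statement is true only of an early reading that the plan never names as the endpoint. For orbital volume, plate contour and operative time it is sound on timing but fails if inclusion item 9 is applied as written. That conclusion assumes that item 9 governs who is analysed; the plan does not say otherwise.

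The likely bias cannot be sized. The documents give no event rates for these three outcomes and no expected loss to follow-up. A reader might take the 25-point and 50-point widths as a measure of this trial's bias, but they are generic illustrations. Nor do the documents support a claim that the primary result is invalid: its measurement time is clear, and its exposure comes only through item 9.

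**What to change.** 1. **Inclusion & Exclusion Criteria:** remove item 9 as a condition for being analysed, and analyse every randomised patient in whom the outcome was measured. Without this step, narrowing the attrition statement would still leave a false sentence.
2. **Randomization Sample Size & Calculation:** limit the attrition statement to orbital volume, plate contour and operative time; delete mydriasis, compartment syndrome and motility.
3. **Outcome definitions:** name one analysis time for each of these three. One workable choice is the already scheduled week-6 visit for motility and mydriasis, and any post-operative assessment for the existing intra-ocular pressure criterion. Report the early reading separately.
4. **Randomization & Statistical Analysis:** add a best/worst-case sensitivity analysis for missing follow-up values. It should cover missed visits for the any-time outcome too, because a patient with no positive reading and a missed visit is not a confirmed non-event.

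The cost is changed wording, one extra analysis and a less favourable statement about attrition. No new visits are needed.

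### The stated imbalance limits (3 per surgeon, 9 overall) do not match blocks of 4, and a fixed, published block size with a list per surgeon and unblinded physicians makes about one third of allocations deducible

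*Combined protocol and SAP*

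**What the plan says.** All of this is in the combined protocol and SAP, under Randomization & Statistical Analysis unless noted.

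- The scheme is pre-generated with a "block size of 4", stratified by surgeon/specialty, and "each surgeon will receive their own list of randomized cases to simplify the logistics of the trial".
- The plan says this guarantees a difference of no more than 3 cases between arms for any one surgeon. From that it concludes that "it is possible but unlikely that there will be a maximum 9 case difference at some" point, and adds that "sizes will be equal at completion".
- On concealment, "the resulting trial arm for each case will be placed in envelopes to be revealed at the time of patient enrollment".
- On blinding, "The treatment will not be blinded to the physician or the patient".
- Randomization Sample Size & Calculation plans 60 cases split evenly, and considers power "if 25% of our expected patient enrollment numbers are not met for any reason".

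The number of lists is not stated. Three is an inference from 9 = 3 × 3 and from the three specialties (OMFS, ENT, Plastic Surgery) named under Preoperative and Postoperative Assessment.

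**The concern.** There are two separate matters.

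**Internal consistency.** The block size and the imbalance limits do not belong to the same scheme, so a reader cannot tell what was generated. The statement about equal final sizes also carries an unstated condition, because the plan gives no rule for closing a list in mid-block.

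**Predictability.** When the last places of a block are forced and the person enrolling can see the earlier assignments, that person can know the next arm before deciding whether or when to enrol a patient. Envelopes hide the next card but do not stop this deduction. The stake is selection bias: patients with a better or worse expected outcome could be directed to one arm. If the baseline balance check passes, outcomes are compared by plain two-sample tests. That check might reveal gross steering after the fact but would not prevent it.

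**Working it through.** **Inputs.** Block size 4, 1:1 allocation, 60 cases, 25% shortfall, 1 cm³ difference, SD 1.17 cm³ and alpha .05 come from the two randomization sections. Two-sided testing and three lists are assumptions.

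**1. The plan's sample size, reproduced.** A two-sample t-test for 1 cm³ with SD 1.17 cm³ and 90% power gives n = 29.76, so 30 per arm and 60 in total (power 90.2%). At 45 cases (22.5 per arm) power is 80.0%. Both figures agree with the plan.

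**2. Running imbalance.** The six orderings of a block are AABB, ABAB, ABBA, BAAB, BABA and BBAA. The largest running difference is 2, reached after AA or BB.

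- Three lists: 3 × 2 = 6.
- A difference of 9 needs at least five lists, since 4 × 2 = 8 < 9.
- Enumerating the 20 orderings of a block of 6 gives a maximum of 3 per list and 3 × 3 = 9 over three lists, which are the plan's two figures.

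**3. Final balance.** If all three lists end on full blocks (for example 20/20/20), the arms are equal for certain. If 60 cases arrive at random over three lists, simulation with blocks of 4 gives a final difference of 0, 2 or 4 in 50%, 46% and 4% of runs. At 45 cases, an odd number, exact equality is impossible. Power is 90.1% at 32/28 against 90.2% at 30/30.

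**4. Predictability.** An allocation is certain once one arm is used up within the block. AABB and BBAA each have 2 such places and the other four orderings have 1 each: (2 × 2 + 4 × 1) / (6 × 4) = 8/24 = 33.3%. Always guessing the arm with more places left, with ties counted as one half, is right in 17/24 = 70.8%. If blocks of 6 were in fact generated, the figures are 25% and 68.3%.

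**5. Illustration of the consequence (all assumed).** Suppose every predictable allocation on every list is steered, and patients steered to the two arms differ by 0.5 cm³ in the outcome.

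- False difference: gap × certain share, or gap × (2p − 1) for best-guess accuracy p.
- SE = 1.17 × √(2/30) = 0.302 cm³; type I error is from the noncentral t with 58 df.
- Certain places only: 0.5 × 0.333 = 0.167 cm³, type I error 8.4%.
- Best guess: 0.5 × (2 × 0.708 − 1) = 0.208 cm³, type I error 10.4%.
- Best guess, but only a quarter of allocations steered: 0.208 / 4 = 0.052 cm³, type I error 5.3%.

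**6. Alternatives, with a tracker who knows the scheme, 20 patients per list.**

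| Scheme | Certain | Best guess | Largest difference per list |
|---|---|---|---|
| Fixed blocks of 4 | 33.3% | 70.8% | 2 |
| Randomly mixed blocks of 4 and 6 | about 6% | about 68.5% | 3 |
| Coin toss, difference capped at 3 | 14.4% | 57.2% | 3 |

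**The case against.** **The limits may be loose rather than wrong.** No more than 3 per surgeon is literally true for blocks of 4, since 2 is no more than 3. That stands for the first sentence only. The plan goes on to infer that 9 is possible, which with three lists it is not.

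**The block size is explicit.** It is stated outright, and 60 cases divide into five blocks of 4 on each of three lists, so 4 is the likelier reading. It is not certain, because both limits fit blocks of 6 exactly. A reader might infer that the true overall limit is 6; the documents do not settle which statement is in error.

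**Equality at completion may mean completed lists.** This is a fair reading, and for such lists the statement is exact. The 45-case scenario comes from a sentence about power that makes no claim of equal arms. What remains is an unstated condition of little consequence.

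**Room for steering is limited.** All patients with orbital fracture are to be offered entry (Human Subject Protections), reconstruction is described as time-sensitive (Background) and some indications call for immediate correction (Inclusion & Exclusion Criteria). Volume is low: 126 fractures in 24 months is 5.25 a month, or 1.75 per list if split equally over three, and not all would be eligible. A list shared by a whole specialty would be harder to track than one surgeon's own. These points stand and reduce the risk. They do not remove it: not every indication is immediate, and the documents do not say who controls the timing of enrolment.

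**A stronger reading is tempting.** A reader might infer that the trial is biased, or that its type I error is 19% to 27%. The documents show no steering. Those figures arise only if every predictable allocation is steered and the patient gap is 1 cm³, the whole design effect. Even at that gap, best-guess steering of a quarter of allocations gives 6.3%.

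**Conclusion.** The point holds, in three parts of unequal weight.

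- **Certain but minor.** With three lists, the stated block size and the stated overall limit cannot both be right. Blocks of 4 give 2 per list and 6 overall; 3 and 9 belong to blocks of 6. The number of lists is inferred.
- **Wording only.** Equal final sizes are conditional on how the lists close. The effect on power is negligible.
- **The substantive part.** A fixed, published block size, separate lists and unblinded physicians make 33.3% of allocations certain in complete blocks of 4 (25% for blocks of 6). This assumes that someone tracks the list. It is an avoidable risk of selection bias whose size the documents cannot establish.

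How far steering by injury size would matter also depends on the outcome. The sample size is built to "compare the difference in contralateral orbital volume between the treatment and control groups", while Study Settings and Patients also defines the primary outcome as the reduction from the post-traumatic volume. Injury size enters the latter directly and the former less so.

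The plan should be changed, but the sample size is unaffected.

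**What to change.** **1. Reconcile first.** Have the statistician check the pre-generated list. State the true block size and the number of lists, and correct the limits to match: 2 per list and 6 over three lists if blocks of 4 were used. Replace the promise of equal sizes with approximately equal, and report the scheme actually used. This is a wording change.

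**2. Then reduce predictability for unused allocations.** Finish the current block on each list, then have the statistician generate a new sequence within surgeon/specialty. There are two options:

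- Randomly mixed blocks of 4 and 6 nearly remove certain predictions (about 6%) but barely lower best-guess accuracy (about 68.5%).
- A coin toss with the difference capped at 3 per list lowers best-guess accuracy more (about 57%, with about 14% certain) but gives looser final balance.

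Remove block sizes and imbalance limits from documents the surgeons see, saying only that allocation is restricted within surgeon/specialty and that the statistician holds the details.

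**Cost of step 2.** It needs new envelopes and a protocol amendment with ethics review, and it allows a running difference of 3 per list instead of 2. With 20 patients per list, final sizes are equal in 53% of trials with mixed blocks and 26% with the capped coin toss, against always with blocks of 4. The worst case at 60 cases is 34/26, with power 89.7% against 90.2%. If the lists are already used up, only step 1 applies.
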